### **Background, Rationale, and Context**

Despite advances in perinatal care in the U.S., maternal mortality has more than doubled over the past two decades, with substantial racial and socioeconomic disparities observed.[1] Hypertensive disorders of pregnancy (HDP) are a leading cause of perinatal morbidity and mortality, with up to 20% of maternal deaths attributed to preeclampsia.[2] In the traditional postpartum care model, many women are not seen for follow-up until six weeks postpartum, with the highest risk women typically scheduled for follow-up three to seven days after discharge. Thus, the postpartum period is a time of particular susceptibility for maternal morbidity and mortality resulting from undiagnosed or inadequately managed HDP.[3] Women from lower socioeconomic status (SES) groups, as well as racial and ethnic minority groups, disproportionately experience an increased risk for adverse consequences from HDP.[4] To mitigate this risk, the American College of Obstetrics and Gynecology (ACOG) recommends blood pressure monitoring (BPM) at 72 hours and through 7-10 days postpartum for women with HDP.[5]

Postpartum readmission for HDP is not limited to antenatally diagnosed HDP; women at “low-risk” account for a significant proportion of readmissions for HDP.[6] ACOG guidelines for postpartum care in lower-risk women recommend an initial postpartum visit by three weeks and a final comprehensive visit by 12 weeks postpartum.[7] However, the majority of readmissions for postpartum HDP occur prior to three weeks, suggesting that this care model is likely inadequate for many women and may contribute to missed or delayed diagnosis and treatment of HDP. In our own, highly diverse patient population, with nearly two-thirds of pregnancies covered by Medicaid or without insurance, compliance with recommended in-person, postpartum visits through this period, among women with higher and lower risk, is less than 50% (internal data).

Given the postpartum risks, women with known HDP experience increased length of stay during their initial postpartum admission.[8] While the increased length of stay has been associated with decreased readmission for HDP, it has also been associated with a significant increase in delivery hospitalization charges.[8] Remote BPM in the postpartum period has been proposed as an intervention to achieve increased monitoring without extending inpatient length of stay.[9]

Several, smaller prospective studies have shown that remote blood pressure monitoring in the postpartum period appears feasible and acceptable in various patient populations, although no studies to date have specifically evaluated feasibility, adherence, and outcomes in lower-income populations. In an RCT

(n=206), Hirshberg et al. demonstrated that remote blood pressure monitoring, coupled with a text-based app providing patient education and real-time provider communication of blood pressure data, resulted in 84% of women receiving recommended blood pressure monitoring.[9] This intervention also reduced racial disparities in receiving recommended follow-up by 50%.[11] Hoppe et al. conducted an experimental study (non-randomized) (n=428) of telehealth with remote blood pressure monitoring that demonstrated a decrease in readmission compared to standard outpatient care.[12] No studies to date have evaluated cost-effectiveness or lower-income populations specifically. In summary, studies have shown the postpartum remote BPM care model to be both feasible and acceptable to patients, with promising evidence from smaller studies for improved patient health outcomes. However, robust, large-scale studies evaluating acceptability and adherence in lower SES populations, clinical outcomes, as well as health care costs are needed to establish the sustainability of this care model.

## **Objectives**

This study is planned to be conducted for a period of 36 months (with an enrollment period of 30 months); however, if it is determined that the following objectives have not been met, the study may be extended based on available funding support.

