### **Primary Objective**

Evaluating remote BP monitoring (rBPM) in a highly diverse patient population for:

- Feasibility and acceptability (patient adherence and satisfaction)
- Increased adherence to ACOG guidelines particularly to evaluate the impact of rBPM on the proportion of women with antepartum/delivery hypertensive disorder with blood pressure measures obtained within 72 hours and seven days of discharge and for all women within three weeks postpartum
- Reduced delivery admission length of stay (LOS)
- Reduced utilization of emergency/acute care services (Emergency Department, OB Triage, Urgent Care)
- Reduced incidence of readmission and readmission LOS
- Assess impact of a rBPM intervention on total health care costs to the patient during the first eight weeks postpartum.

Comparisons:

- rBPM relative to usual standard of care (SOC)
- Performance within racial and socioeconomic subgroups

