### **Sample Size**

It is estimated that approximately 5,000 women will deliver in Forsyth County over a 30 month time period. Of these, we anticipate that approximately 2000 women will be randomized equally (1000 in each study arm) during this time period.

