### Secondary:

Remote BPM will decrease the duration of stay in the postpartum unit, with women with remote BPM discharged earlier than those with usual care, with a median, absolute decrease of length of stay of >1 day(s), irrespective of insurance status.

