### Secondary:

Readmissions for HDP, within eight weeks of discharge, occurs in ~2% of the general patient population.[4,8] We hypothesize an absolute decrease of 60% in readmission rates. With earlier intervention, we hypothesize that the median length of stay for the readmission will be significantly reduced in the intervention arm.

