## **Health care costs**

### Primary:

We hypothesize >50% average total cost reduction (charges and amount paid, examined separately), for the period from discharge through eight weeks postpartum, for the intervention versus usual care arm, irrespective of insurance status.

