## **Analytical Plan**

The subject will complete a baseline demographic questionnaire at the time of enrollment. This questionnaire will be completed electronically through a unique link via REDCap. Additionally, subjects in the rBPM study arm will be asked to complete a post-study questionnaire electronically through a unique link via REDCap ~ 1 week after subject has completed the study.

The following EHR-based clinical measures will be obtained from each subject:

- Demographics
- History of hypertension or use of blood pressure lowering agents
- Pregnancy-related data (e.g. blood pressure, pre-pregnancy BMI, weight gain, complications, pre-pregnancy diabetes, gestational diabetes, delivery complications)
- Birth outcomes, including gestational age at delivery, cesarean or vaginal delivery, singleton or multiparous delivery, birth weight
- Length of stay of admission and any readmissions through 12 weeks postpartum
- Use of blood pressure lowering agents through 12 weeks postpartum

We will link EHR, BP, baseline demographic questionnaire data, billing, and user satisfaction data to inform study questions as described above. Data will be reviewed for missingness, with multiple imputation performed as appropriate. Initially, data will be analyzed using descriptive statistics. Comparison between groups may be performed using chi square tests for proportions, and t-tests or ANOVA procedures for continuous variables. Crude and adjusted regression analysis will be performed to identify independent outcome predictors. Other inferential statistical analysis will be conducted as appropriate.

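### The extension clause does not exclude extending because a result was not seen, and the five between-arm outcomes labelled primary have no order, alpha or adjustment

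*Combined protocol and SAP*

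**What the plan says.** The Objectives section of the combined protocol and SAP plans 36 months, 30 of them for enrolment, and adds that "if it is determined that the following objectives have not been met, the study may be extended based on available funding support". It gives no maximum size, decision date, decision-maker, blinding of the decision or alpha adjustment.

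The Primary Objective follows. Under the lead verb of evaluating, it lists higher guideline adherence, shorter delivery stay, less acute care use and "Reduced incidence of readmission and readmission LOS".

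The outcome sections label some of these items differently:

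| Item | Primary Objective | Outcome sections |
|---|---|---|
| Delivery LOS | listed | Secondary: "Remote BPM will decrease the duration of stay in the postpartum unit" |
| Readmission and its LOS | listed | Secondary: "We hypothesize an absolute decrease of 60% in readmission rates" |
| Satisfaction | listed | Secondary |
| Emergency and acute care use | listed | no primary or secondary label |

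Five between-arm comparisons are labelled primary. Three concern blood pressure (BP) ascertainment (Clinical outcomes): a reading within 72 hours and monitoring through 10 days, both in women with a hypertensive disorder of pregnancy (HDP), and a reading within three weeks in all women. Two concern cost (Health care costs): "We hypothesize >50% average total cost reduction", with charges and amount paid examined separately.

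The Analytical Plan says "Comparison between groups may be performed using chi square tests for proportions, and t-tests or ANOVA procedures for continuous variables". It states no alpha, sidedness, test order, multiplicity rule or interim analysis. The Sample Size section gives 2,000 women as an anticipated number, without a power calculation.

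**The concern.** An extension triggered by recruitment does no harm to the error rate. An extension triggered by a disappointing comparison, followed by another test at the full level, gives each outcome a second chance to cross 5%. The clause permits the first and does not rule out the second.

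The labels are a separate matter. With two lists that disagree and no ranking, the set of primary tests is not fixed, so the emphasis could be settled after the results are known. The five tests that are labelled primary have no joint error control.

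Readmission shows where a wish to extend is most likely. It is rare, and the trial is not large for it, so a non-significant result is quite possible even if the hoped-for effect is real.

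**Working it through.** **Inputs.** From the documents: 2,000 women, 1:1; five between-arm primaries (three BP, two cost); 60% versus 90% for monitoring in HDP women; about 2% readmission. Assumed: two-sided 5% per test, since none is stated; the extension sizes; the correlations between tests. The plan has no error rate or power figure of its own to reproduce.

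**1. Extension after a non-significant result, one outcome.** Test at n1 = 2,000. If not significant, extend to n2 and test all the data again at 5%. Under the null the two Z statistics are bivariate normal with correlation √(n1/n2), and type I error = P(|Z1| > 1.96 or |Z2| > 1.96).

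| Extension | n2 | Correlation | Type I error |
|---|---|---|---|
| +25% | 2,500 | 0.894 | 7.1% |
| +50% | 3,000 | 0.816 | 7.7% |
| +100% | 4,000 | 0.707 | 8.3% |

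The constant nominal level at both looks that restores an overall 5% is about 0.035, 0.032 and 0.029 respectively. If the decision uses only recruitment counts or pooled blinded data, no adjustment is needed.

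**2. Five primary tests, no extension.**
- Independent, all five nulls true: 1 − 0.95^5 = 22.6%. For jointly normal statistics this is the ceiling.
- Pairwise correlation 0.5, all null (simulation): about 18%.
- The three BP effects real, only the two cost tests null: 1 − 0.95² = 9.8% if independent, and 7.8% or 7.0% at an assumed correlation of 0.8 or 0.9. Hence about 7-10%.

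**3. Readmission.** An absolute fall of 60 points from 2% is impossible, so the stated decrease is read here as relative: 2% to 2% × 0.4 = 0.8%. With 1,000 per arm and pooled rate 1.4%:

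z = [0.012 × √1000 − 1.96 × √(2 × 0.014 × 0.986)] / √(0.02 × 0.98 + 0.008 × 0.992) = 0.32, so power is about 63%.

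The chance of a non-significant result under the hoped-for effect is therefore about 37%; 80% power would need 1,504 per arm.

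**4. What stricter control would cost the BP outcomes.** For 60% versus 90%, the same formula gives 89% power with 40 per arm at 5%, and about 99% with 100 per arm at 1% (the strictest Holm step for five tests, 0.05/5). The HDP share is not given. If it were only 10% (assumed), there would be 100 such women per arm. The planned all-women difference, 30% versus 90%, is larger still. The same check cannot be made for the cost outcomes, because no variance is given.

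**The case against.** A reader might infer that the protocol plans to look at results by arm and to carry on until they are favourable. The documents do not support that. The extension sentence opens with study length and enrolment period and makes extension depend on funding. The Primary Objective is introduced as evaluating, its cost item is to assess an impact, and the Secondary Objective concerns a risk algorithm and planning. An evaluation objective is met once the evaluation is done. No interim comparison by arm and no second test is described. This stands, so the 7-8% figures are conditional. What does not follow is that the clause is harmless: nothing in it limits the trigger to recruitment, and the directional items are among the objectives it refers to.

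A reader might also infer that the conflicting labels themselves inflate error. They do not. A secondary outcome can serve a primary objective, and the more specific outcome sections put LOS and readmission as secondary. The conflict leaves the primary set unclear; any inflation comes from multiple unadjusted tests.

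Third, 22.6% could be taken as the expected error. It is near the worst case. The 72-hour and 10-day outcomes are measured in the same women, who also count in the three-week outcome. Charges and amount paid describe the same care. An arm given cuffs and reminders may well show a real BP-ascertainment effect. That objection is sound, and it is why a range is reported. Readmission and LOS are also not among the five tests counted.

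**Conclusion.** The concern holds in a limited form. The extension rule is open to an outcome-driven reading that the text should exclude. If it were used that way without adjustment, type I error per outcome would rise from 5% to about 7.1-8.3%. If extension depends only on recruitment, there is no inflation.

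Independently of the clause, the five between-arm primaries have no stated error control. The familywise figure runs from about 7-10% (BP effects real, only the cost tests null) through about 18% (all null, correlation 0.5) to 22.6% (all null, independent).

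All these figures rest on an assumed two-sided 5% per test. The mismatch between the Primary Objective and the outcome labels is a matter of fact; its consequence is an undefined primary set, not a quantifiable inflation.

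**What to change.** 1. **Extension clause (Objectives).** State that enrolment may be extended only if the planned 2,000 women have not been randomised by month 30, or the study period extended to complete follow-up, and that the decision is made without sight of outcomes by arm. If the sponsor wants to be able to extend on results, prespecify an alpha-adjusted design with a maximum sample size.
2. **Labels.** Make the Primary Objective agree with the outcome sections: LOS and readmission secondary throughout, one label for acute care use, and the satisfaction mismatch settled in the same edit.
3. **Multiplicity (Analytical Plan).** State an overall two-sided 5% and treat the five between-arm primaries as one family. Use either Holm across all five, or a fixed sequence that starts from one BP-ascertainment outcome. Which one is the sponsor's choice; the documents do not rank them. A single primary at 5% beside a separate, ungated Holm family of the other four at 5% would not suffice: if independent and all null, 1 − 0.95 × (1 − 0.0125)^4 = 9.7%.

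These are wording changes. The cost is the freedom to extend on results and some loss of power for the two cost outcomes, which cannot be sized from the documents. The BP outcomes lose almost nothing at the planned differences of 30 to 60 points.

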### **Primary Objective**

Evaluating remote BP monitoring (rBPM) in a highly diverse patient population for:

- Feasibility and acceptability (patient adherence and satisfaction)
- Increased adherence to ACOG guidelines particularly to evaluate the impact of rBPM on the proportion of women with antepartum/delivery hypertensive disorder with blood pressure measures obtained within 72 hours and seven days of discharge and for all women within three weeks postpartum
- Reduced delivery admission length of stay (LOS)
- Reduced utilization of emergency/acute care services (Emergency Department, OB Triage, Urgent Care)
- Reduced incidence of readmission and readmission LOS
- Assess impact of a rBPM intervention on total health care costs to the patient during the first eight weeks postpartum.

Comparisons:

- rBPM relative to usual standard of care (SOC)
- Performance within racial and socioeconomic subgroups

### **Secondary Objective**

Evaluate the performance of a recently developed risk stratification algorithm for predicting postpartum readmission due to complications of high BP [13]. With the rBPM measures, we can examine patient demographic factors associated with developing abnormal BP readings postpartum, and not just those that were recognized because of being readmitted.

- Improve risk stratification
- Inform sustainability planning

## **Methods and Measures**

This is a randomized control trial (RCT). All women, 18 years of age and older, who have delivered or are planning to deliver an infant(s) at The Birth Center at Atrium Health Wake Forest Baptist (AHWFB) and reside in Forsyth County will be eligible for enrollment and invited to participate in the SMART- BP study. We will enroll women during the prenatal period as well as after delivery. A member of the study staff will review the daily OB prenatal clinic schedules at all 3 AHWFB locations (Downtown Health

Plaza, Clemmons Plaza, and Shepherd Street) to screen patients for eligibility. The study staff member will then notify the designated clinic staff of eligible patients that should be offered the opportunity to watch the SMART-BP informational video (with Spanish language closed captioning available-*Appendix 10*) at some point during a clinic visit occurring at  $\geq$  24-weeks gestation. A clinic staff member will provide an iPad that the patient can watch the video on, if the patient is in agreement. The video is approximately 8 minutes in length. After viewing the video, the patient will then be offered an opportunity to contact a study staff member (via email) to answer any questions they may have, to decline enrollment, or they can choose to review the electronic consent form via REDCap and sign if they wish to enroll in the study. A copy of the consent form will be sent to them via email at the time of enrollment.

If an eligible patient received postpartum care in The Birth Center and was not previously provided the opportunity to view the SMART-BP informational video at a prenatal clinic visit, she will be offered the opportunity to view the video in her hospital room prior to discharge from the postpartum unit. After viewing the video, the patient will then proceed through the same enrollment process that is provided to women at their prenatal visit. A Nurse Education and Support Team (NEST) Coordinator would then be able to randomize the subject using REDCap and then inform the subject which study arm they had been assigned. In the event a subject was enrolled in a prenatal clinic, randomized to the rBPM arm and was discharged from the hospital following delivery without receiving a BP cuff/monitor and instructions from a NEST coordinator (on weekends, and designated holidays), a BP cuff/monitor and printed instructions would be delivered to the subject by a courier service (Delivery On Time). A NEST coordinator would then contact mom via phone as soon as feasible (within 48 hours) to review instructions and ensure the subject was able to download the BabyScripts app and was able to record a BP measurement.

Patients who were not offered the opportunity to enroll in the study at a prenatal clinic visit, delivered an infant(s) at The Birth Center, and were discharged or were otherwise not approached for an initial visit by a NEST Coordinator will not be included in this study.

After obtaining electronic consent via REDCap, the subject will be asked to complete a baseline demographic questionnaire (*Appendix 1a and 1b*). After this brief questionnaire is completed, the subject will then be randomized into one of two study arms; either rBPM or SOC. Study ID numbers will be assigned to each subject. Randomization assignment will be completed by a study staff member using the REDCap randomization tool after enrollment and after the subject has completed the baseline questionnaire in REDCap or in real time if the subject is enrolled in the hospital after delivery. All subjects have an equal chance of being assigned to either the rBPM or SOC study arm. The study arm assignment will be documented in the subject's EMR. The subjects that were enrolled during a prenatal clinic visit will not be aware of their study arm assignment until after they have delivered their infant(s) at The Birth Center. Logistically, it is not feasible to complete the randomization in real-time in the outpatient setting, and there are no study activities that occur between the time of the subject's outpatient prenatal clinic visit and their delivery at The Birth Center.

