### **Subjects selection criteria**

### **Inclusion Criteria**

- Women that received prenatal care at one of the AHWFB OB/MFM outpatient clinic locations (Downtown Health Plaza, Clemmons Plaza, and Shepherd Street)
- Women that delivered an infant(s) at The Birth Center at AHWFB
- Women that delivered an infant(s) at home or outside facility, and were transported to AHWFB and received postpartum care in The Birth Center
- Currently resides in Forsyth County, NC
- 18 years of age or older
- Able to read and understand either English or Spanish
- Owns or has daily access to a smartphone (iOS or Android operating system) and Wi-Fi or monthly mobile data plan

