### **Interventions and Interactions**

After obtaining informed consent electronically via REDCap, all subjects will be asked to complete a questionnaire using REDCap in order to collect baseline demographic data. Collecting this demographic data directly from the subject is to ensure accuracy. It has been reported that race, ethnicity, and even preferred language data may be missing from a subject's EMR or may have been previously entered into the EMR incorrectly (internal report). Additionally, collecting data on the subject's education level and marital status may help inform health disparities among various subject groups.

The subject will be directed to the demographic questionnaire after signing the electronic consent form via REDCap. The questionnaire must be completed in order to randomize the subject to a study arm. It is estimated that it will take  $\leq 5$  minutes to complete the baseline questionnaire. The baseline questionnaire will be available in both English and Spanish.

The subjects randomized to the rBPM study arm will receive a specialized Bluetooth enabled BP cuff/monitor from a NEST Coordinator in the hospital after delivery and before they are discharged home. The subject will receive both verbal and written education (in the subject's primary language) on the correct use of the specialized BP cuff/monitor. (*Appendix 7a and 7b*). The BabyScripts app will be downloaded on the subject's personal smartphone utilizing either an iOS or Android operating system. Instructions on the use of the BabyScripts app will be provided verbally and in writing (in the subject's primary language). The data entered into the BabyScripts app by the subject includes the following: name, email, DOB, cell phone number, pre-pregnancy weight, height, and date of (actual or expected) hospital discharge following delivery. The subject's pre-pregnancy weight and height are utilized by the app to calculate the subject's BMI, which will then help to identify the correct size of BP cuff that the

subject should be using for this study. Using an oversized or undersized BP cuff can result in erroneous BP measurements. The BabyScripts app is downloaded at no cost to the subject. Per the Master Agreement with BabyScripts, BabyScripts does not sell or share any personal data collected through the app.

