The subject's education/training for participating in this research study is expected to take approximately 10 - 15 minutes, but the amount of time needed may vary based on the individual subject's level of understanding. After completing the training, a NEST Coordinator must observe a successful subject-directed trial of the rBPM equipment and app. The NEST Coordinator will document any identified barriers that may limit the subject's successful participation in the study.

The subject will use the specialized BP cuff/monitor to measure their BP twice-daily beginning on the morning of the day following hospital discharge. This day will be noted as "Day 1". Twice daily BP monitoring will continue through Day 16. Then, starting on Day 17, the subject will need to obtain their blood pressure only once daily in the morning, and continuing daily through Day 21. Subject's BP measurements will no longer be transmitted via BabyScripts app beginning on Day 22. The subject will receive a reminder text via the BabyScripts app when it is time to obtain their BP. Due to the limitations for customization, the Babyscripts reminder notifications will be sent twice daily (one in the morning and once in the evening) for the entire 21 day study period. . It is expected that it will take the subject less than 5 minutes (after a 5-10 minute rest period that is recommended to for the most accurate reading) to obtain each BP measurement. The subject's BP measurements, and any alerts are sent in real-time to a secure cloud-based portal. If the subject's BP falls within the normal range ( $\leq 140/90$ ), they will receive notification via the BabyScripts app, that their BP reading is normal. Any clinically relevant BP readings (defined below) will initiate an alert to the BabyScripts call center staff, who then communicates directly with a member of AHWFB Maternal-Fetal Medicine (MFM) staff. An assigned (or on-call) MFM staff member is available for response 24/7/365. While BabyScripts acts in real-time to alert the provider, any issues with wait time, unanswered phone lines, etc. may lead to delays to when the subject can expect to hear from the provider. Alert calls received from BabyScripts are documented in the subject's EMR.

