### **Feasibility and acceptability outcomes**

#### Primary:

Among those randomized to the intervention arm, at least 90% will have a smartphone and will be able to have the remote BPM app loaded onto their phone, prior to discharge. We hypothesize an absolute difference of no more than 10% (e.g., 85% vs 95% with a smartphone) according to insurance status (Medicaid or uninsured vs. private insurance).

Remote BPM will be successfully integrated into patient care as evidenced by at least 90% adherence to a median of at least one blood pressure reading/day for three weeks and 70% adherence to obtaining a median of two blood pressure measures for initial 2 weeks postpartum. We hypothesize an absolute difference in adherence, according to patient insurance status of <15%.

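### The app-loading feasibility criterion is not aligned with the planned courier route, under which some rBPM women are set up only after discharge

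*Combined protocol and SAP*

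**What the plan says.** **The default.** Interventions and Interactions has rBPM women receive the cuff "from a NEST Coordinator in the hospital after delivery and before they are discharged home". After training, "a NEST Coordinator must observe a successful subject-directed trial of the rBPM equipment and app". The rBPM arm section also wants the demonstration done before discharge, partly to confirm cuff size. None of these statements carries an exception.

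**The exception.** Methods and Measures covers women enrolled in a prenatal clinic, randomised to rBPM and discharged on a weekend or designated holiday without a coordinator visit. For them, "a BP cuff/monitor and printed instructions would be delivered to the subject by a courier service (Delivery On Time"). Next, "A NEST coordinator would then contact mom via phone as soon as feasible (within 48 hours"), to go over the instructions and "ensure the subject was able to download the BabyScripts app and was able to record a BP measurement". Subject Recruitment Methods confirms that coordinators' inpatient visits take place only on weekdays. No courier deadline is given, and the start of the 48 hours is not stated.

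**The criterion.** The primary entry under Feasibility and acceptability outcomes takes everyone randomised to the intervention as its denominator. It expects at least 90% to have a smartphone and says they "will be able to have the remote BPM app loaded onto their phone, prior to discharge". It also hypothesises an absolute difference of no more than 10% by insurance status. The courier route is not mentioned.

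**Entry.** The inclusion criteria already require that a woman "Owns or has daily access to a smartphone (iOS or Android operating system) and Wi-Fi or monthly mobile data plan".

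**The concern.** The protocol plans for some intervention women to be set up at home, then measures feasibility by what was possible before they left hospital. A woman who receives her cuff, loads the app and records a reading at the follow-up call has been served as Methods and Measures intends, yet normally counts against the criterion.

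The entry criteria sharpen this. Because a smartphone with Wi-Fi or data is required, few randomised women should fail for lack of a device. What can still fail is loading the app in time, and that depends partly on whether a coordinator was on the unit. A shortfall could then be read as a problem of access or ability when part of it is weekday staffing. The plan has no field that separates the two, either overall or in the insurance comparison.

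**Working it through.** **Inputs from the documents.** Target: at least 90% of the rBPM arm. Planned arm size: 1,000. Coordinator visits: weekdays only. Not given: the share enrolled prenatally, the share discharged without a coordinator visit, and the loading rate expected among women who are met. The 90% is a stated expectation, so there is no calculation of the plan's to reproduce.

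**Step 1: break-even.** Let f be the courier share of the rBPM arm and s the loading rate among women met in hospital. On the plain reading, courier women count as failures:

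proportion loaded before discharge = (1 − f) × s

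Setting this to 0.90 gives f* = 1 − 0.90/s.

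- s = 100%: f* = 1 − 0.90/1.00 = 10.0%, about 100 of 1,000 women
- s = 98%: f* = 1 − 0.90/0.98 = 8.2%, about 82 women
- s = 95%: f* = 1 − 0.90/0.95 = 5.3%, about 53 women

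**Step 2: plausible range for f (assumptions).** Write f = q × w, where q is the prenatally enrolled share of the arm and w the share of those women discharged without a visit. I take w from 5% to 2/7 = 28.6%. The upper end counts every weekend discharge under an even weekly spread. It is high, because some of those women will have been met on a weekday.

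| q | w | f | Best possible (s = 100%) | s = 95% |
|---|---|---|---|---|
| 50% | 5% | 2.5% | 97.5% | 92.6% |
| 50% | 10% | 5.0% | 95.0% | 90.25% |
| 75% | 10% | 7.5% | 92.5% | 87.9% |
| 25% | 28.6% | 7.1% | 92.9% | 88.2% |
| 50% | 28.6% | 14.3% | 85.7% | 81.4% |

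The result falls on either side of 90% depending on two shares that the documents do not give.

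**Step 3: what the failures are made of.** Staffing share of failures = f / [f + (1 − f)(1 − s)]. With f = 5% and s = 95%: 0.05 / (0.05 + 0.95 × 0.05) = 0.05/0.0975 = 51%. Even where the target is just met, about half the recorded failures would reflect the day of discharge.

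**Step 4: how much the counting rule matters.** Let c be the share of courier women whose app is confirmed at the call. A proportion that counts them is (1 − f)s + fc. With f = 10% and s = c = 95%, the criterion as written gives 0.90 × 0.95 = 85.5%, and the second proportion gives 85.5% + 0.10 × 95% = 95.0%. The same delivery of care falls below or above 90% according to a rule the plan does not set.

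**Step 5: the other reading.** The criterion speaks of being able to have the app loaded. Read as capability, courier women need not fail. But nobody tests them before they leave, so the plan collects nothing on which to score them.

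**The case against.** The courier route is a deliberate and sensible contingency, and its call already verifies the app and a reading. Outcome Measures defines feasibility as that of administering the intervention, so missing women at weekends is a genuine delivery result. The 90% is a hypothesis with no decision rule attached. Interventions and Interactions already has coordinators document barriers to participation. All of this stands. It is why the proportion as written should be kept and why the request is an addition. It does not supply a counting rule. The barrier record is described alongside the in-person training that these women miss, and it has no coded categories.

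Four stronger inferences are tempting, and the documents do not support them.

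- **That the route breaks the Day 1 start.** Readings are due "beginning on the morning of the day following hospital discharge", but no courier time is stated and same-day delivery would meet this. Nor would short delays move the adherence targets, which rest on medians. Losing the first 3 days removes 6 of 37 scheduled readings (16 × 2 + 5 × 1 = 37), yet leaves an otherwise adherent woman with a median of 2 a day over 14 days. That median drops below 2 only at 7 lost days.
- **That the 72-hour blood pressure comparison is compromised.** That endpoint concerns women with hypertensive disorders, who by the Background section stay longer and so are more likely to be met on a weekday. Any size put on the effect would rest on assumed inputs.
- **That the insurance comparison is biased.** Nothing says that weekend discharge or prenatal enrolment differs by insurance status. The plan simply could not show whether it does.
- **That unit nurses should hand over the kits.** Handing over a cuff does not load the app, and the protocol gives those nurses no study role.

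**Conclusion.** The point holds as a minor misalignment in a primary feasibility criterion. A planned set-up route normally produces failures on the plain reading, and women never tested on the capability reading.

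Whether the 90% target would be missed is possible but not shown. The break-even courier share is 10.0%, 8.2% or 5.3% of the arm for in-hospital loading of 100%, 98% or 95%. These limits follow from the target alone, given that courier women count as failures; where the trial sits relative to them depends on shares the documents do not state. What is at stake is what the feasibility result can be taken to mean. Randomisation, the adherence targets and the clinical comparisons are not called into question.

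**What to change.** **(a) Feasibility and acceptability outcomes.** Report the proportion as written. Beside it, report a second proportion with the same denominator, all women randomised to rBPM, counting app loading confirmed at the follow-up call as success. Extend the existing barrier documentation to a coded reason for not loading before discharge: no coordinator contact; no phone or data; unable. Show the reasons by insurance status as well. Settle this before results are seen.

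**(b) Methods and Measures.** Run the 48 hours from discharge. Have the courier deliver no later than the day after discharge. Add a cuff-size check to the call. The protocol uses the app's BMI and the in-hospital demonstration to get the size right, and it describes neither step before a couriered cuff is sent.

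**Cost.** One extra data field and one extra table row. The documents do not say whether coordinators telephone at weekends. A Saturday-morning discharge puts the 48-hour limit at Monday morning, so over a holiday Monday the call would either be made on a non-working day or be recorded as late.
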